##### **4.6.1 Lost-to-Follow-up:**

If the participant misses the scheduled follow-up time point and the attempts at contacting the participant detailed below are unsuccessful, then the participant is considered lost to follow-up. Study personnel shall make all reasonable efforts to locate and communicate with the participant (and document these efforts in the source documents), including the following, at each contact time point:

- A minimum of 2 telephone calls or emails on different days over a 10-day period to contact the participant should be recorded in the source documentation, including date, time and initials of study personnel trying to make contact.
- If these attempts are unsuccessful, a certified letter should be sent to the participant. The letter will request the participant to contact the Investigator. Study staff will also request return of the Zio monitor to iRhythm as soon as possible.

#### **4.7 Number of Participants Required to be Included in the Study**

A total of up to 150 participants will be included in the study.

#### **4.8 Estimated Time Needed to Enroll this Number**

It is anticipated that it may take up to 16 weeks to enroll all required participants.

#### **4.9 Expected Duration of Each Participant's Role**

The expected duration of participation is approximately 30 days.

#### **4.10 Total Expected Duration of the Study**

The time to complete the Study is estimated to be approximately six months (four months to complete participant enrollment, one month follow-up and one month to complete analysis and generate the study report).

#### **4.11 Study Participant Completion**

A participant is considered to have completed the study when any of the following has occurred:

- The participant is considered lost to follow-up per the above definition
- The participant withdraws consent
- The Investigator withdraws the participant from the Study

- The participant has died
- The Study has been completed (e.g., the participant's 30-day or final follow-up time point has been reached)
- The patch has prematurely detached from the participant (in the case of early detachment the participant should notify study staff of the date and time of detachment, and a study completion visit will be scheduled)
- The Sponsor has terminated the Study.

Sponsor must be notified of the reason for participant discontinuation. Investigators must also report this to their IRB, as required. Participants will not be replaced.

## 5.0 BASELINE VISIT AND FOLLOW-UP ASSESSMENTS

### 5.1 Baseline (Visit 1)

During the Baseline visit (Visit 1) the participant will be consented, and the informed consent process will be documented prior to patch application. Additional activities include:

Baseline health and demographic information:

The following information will be gathered from each participant in order to establish representation of the population and includes minimum:

- Medical Background/History as reported by the participant, including:
  - Cardiac Disease History
    - Including indication for monitoring if enrolled at a clinical care site
  - Skin characteristics as reported by the participant
    - Skin Type (e.g., dry, oily, or normal)
    - Hyperhidrosis Status (e.g., primary, secondary, or none – see definitions in appendix )
    - Fitzpatrick Skin Type (e.g., Type I-VI) – using the Fitzpatrick Skin Type assessment questionnaire completed by the participant
    - Chest Hair Density by visual inspection (e.g., smooth/no hair, some hair, moderately hairy, or very hairy) in the target patch placement area
- Demographic Information
 

– Age	– Sex at birth
– Race	– Ethnicity
– Weight	– Height

Patch application:

The Zio monitor will be applied to the participant's left upper chest/pectoral region and may be completed by either the participant (self-application) or by a Health Care Provider (HCP) or designee (i.e., the Study Coordinator or cardiac technician). There are two phases to this study. The application process for the first 75 study participants was conducted as outlined in the Zio Monitor Instructions for Use – LB10262.A. All 75 study participants have been enrolled as of 28 February 2025. Phase two of enrollment will include an additional 75 study participants using an updated skin prep process, the formal labeling instructions are not yet finalized pending the outcome of this study, but the following steps will be utilized in phase two:

- Identify the area of skin to be prepared for application.
- Shave the area for all genders even if there is no visible hair present.
  - Proceed with shaving

- Wipe away the hair shavings
- Make sure the skin is dry before continuing
- Exfoliate the area with 20 strokes to remove dead skin.
  - 10 strokes up and down, 10 strokes left to right
  - If discomfort occurs, decrease the pressure of the strokes
- Clean the prepared skin with the alcohol wipe.
- Wait one minute for the skin to dry. Study Staff to take a photo of the prepared skin
- Proceed with applying the Zio monitor.
- Study Staff to take a photo of the skin after the Zio monitor has been applied.

During the Baseline visit, participants will either have a patch applied by a Study Staff member (i.e., Study Coordinator) or participants will self-apply the patch to simulate home enrollment. In the event of self-application, the study participant will open the Zio monitor kit and the Zio monitor instructions for application and will self-apply the device in the presence of a Study Staff member. The Study Staff member is allowed to provide some guidance, but every effort should be made to allow the participant to place the patch without intervention from the Study Staff.

If there is an issue with the device after initial placement (e.g., device fails to activate), the device will be removed and a 2nd device may be applied. In the case that a 2nd device is required, the shaving and exfoliation steps may be skipped, but the alcohol wipe and drying step will still be completed.

## 5.2 Patch Wear Period

All consented participants in whom the Zio monitor Patch application is attempted will be considered enrolled in the study. Patch application is considered to have been attempted when the Zio monitor Patch kit is opened and the first step necessary for skin preparation has been initiated. The participant will be instructed to wear the device for as long as possible, up to the 30-day visit.

Study participants will be instructed to press and hold along the edges of the patch if they notice the patch peeling or lifting at the edges during the wear period. If a patch completely detaches from the participant's chest, the patch will not be re-applied. In the case of early patch detachment, the participant should notify study staff of the date and time of detachment, and a study completion visit should be scheduled as soon as possible.

At any time after patch application, if the device is determined to no longer be functioning (for example, if a rapidly blinking orange light is observed), the device will not be replaced. The date and time the determination of function failure will be noted as close to accurate as possible. As a non-functioning device does not present a safety concern, the participant will be asked to continue wearing the non-functioning patch for as long as possible, in order to record wear duration and wear experience data.

## 5.3 Protocol Required Medications

There are no protocol required medications for this study, and no medications will be administered for the study. A complete list of current medications will not be requested during the Baseline visit. However, medications used to treat an adverse event will be captured.

## 5.4 7-Day and 14-Day ( $\pm$ 3 days) Participant (Phone Call or Video Visit 2 & 3)

A phone call or video call at days 7 and 14 will be conducted in order to assess the status of the participant and the patch adherence.

### **5.5 21-Day (+3 days) Participant Follow-up (Visit 4)**

At day 21 following patch application and up to day 24, participants will be asked to return to the clinic and the following activities will be conducted:

- Skin assessment by HCP or designee, including photograph of the area of the device
- Adverse Event review
- Answering of any questions and verification of ongoing consent to study participation

### **5.6 30-Day (±3 days) Participant Follow-up (Visit 5)**

At day 30 following patch application and up to day 33, participants will be asked to return to the clinic and the following activities will be conducted:

- Skin assessment by HCP or designee, including photograph of the area with the device on and also upon device removal
- Adverse Event review
- Zio patch removal and visual inspection, including photograph of front and back of patch
- Patch return to iRhythm Technologies, Inc. for data download and evaluation

Participants who applied the Zio to themselves at the Baseline visit will be asked to remove the patch. They may ask a Study Staff member to provide guidance in the removal process.

Study clinical assessments and activities are summarized in **Table 2**.

Table 2: Clinical Assessment Schedule

Required Assessments to be Collected	Baseline (Visit 1)	7 & 14-Day (Visit 2 & 3)	21-Day (Visit 4)	30-Day (Visit 5)
		±3 days Phone or Video Call only	+3 days	±3 days
Informed Consent 	X	X	-	-
Medical and Cardiac Background/History	X	-	-	-
Fitzpatrick Skin Assessment	X	-	-	-
Skin Condition Assessment  , Including photograph(s)	X	-	X	X
Assessment of Device Adhesion Performance, Including photograph(s)	-	-	X	X
Adverse Events 	X 	X	X	X

1. *Continued Informed Consent will be verified at each post-baseline contact.*
2. *Including chest hair density, as applicable.*
3. *Adverse Events include serious adverse events, all device-related complications, device deficiencies, device malfunctions, procedures and any hospitalizations. If AEs are ongoing at the 30-day visit, the participant should be contacted until resolution, or Day 37, whichever is sooner.*
4. *AEs are only assessed following Informed Consent and participant enrollment into the study.*

The study device will be returned to iRhythm Technologies, Inc. for download and analysis of the ECG signal collected during the wear.

Upon completion of study follow-up, all devices will be retrieved from study participants and returned to the Sponsor for analysis. Devices will be processed through the algorithm and reviewed by a clinical research qualified cardiac technician. The preliminary report will be provided to a Safety Committee and reviewed by a licensed cardiologist for finalization and determination of any safety concerns. A copy of the report will also be provided to the participant for their medical records and to share with their personal physicians.

NOTE: Following data retrieval from the Zio patch, the patch will be provided to Research & Development (R & D) for further review and inspection. Any reporting from potential findings from the device inspection by R & D is separate from this study protocol and out of scope.

## 6.0 ADVERSE EVENTS

Adverse events will be monitored and reviewed with the Study Investigator to determine any necessary action. To comply with standards and guidelines on clinical study adverse event reporting, the following standard definitions and reporting timelines will be adhered to for this study.

## 6.1 Definitions

### 6.1.1 Adverse Event

An adverse event (AE) is any untoward medical occurrence, unintended disease or injury, or untoward clinical signs (including abnormal laboratory findings) in participants, users or other persons, whether or not related to the medical device. It is anticipated that arrhythmias will be noted on the scans. These are not considered adverse events and do not require reporting unless they have caused an adverse event (i.e., rapid atrial fibrillation is noted on scan, during this time the subject had a syncopal episode that resulted in bruising. The atrial fibrillation is not the AE but the syncopal episode is an AE and must be reported).

For this study AEs will be defined as follows:

- Mild: Transient or mild discomfort; no limitation in activity; no medical intervention/therapy required.
- Moderate: Mild-to-moderate limitation in activity, some assistance may be needed; no or minimal medical intervention/therapy required.
- Severe: Marked limitation in activity, some assistance usually required; medical intervention/therapy required, hospitalizations possible.
- Life-threatening: Extreme limitation in activity, significant assistance required; significant medical intervention/therapy required hospitalization or hospice care probable.

### 6.1.2 Serious Adverse Event

If the AE meets any of the criteria below, it is regarded as a serious adverse event (SAE) and is required to be reported according to the FDA guidelines for SAE reporting.

- a) Led to a death,
- b) Led to a serious deterioration in health that either:
  - 1) Resulted in a life-threatening illness or injury, or
  - 2) Resulted in a permanent impairment of a body structure or a body function, or
  - 3) Required in-patient hospitalization or prolongation of existing hospitalization, or
  - 4) Resulted in medical or surgical intervention to prevent life threatening illness or injury or permanent impairment to a body structure or a body function.
- c) Led to fetal distress, fetal death or a congenital abnormality or birth defect.

An important medical event that may not result in death, be life-threatening, or require hospitalization but may be considered serious when, based upon appropriate medical judgment, may jeopardize the participant and/or may require intervention to prevent one of the outcomes listed in this definition may also be considered an SAE.

**Note 1:** This includes device deficiencies that might have led to a serious adverse event if a) suitable action had not been taken or b) intervention had not been made or c) if circumstances had been less fortunate. These are handled under the SAE reporting system.

**Note 2:** A planned hospitalization for pre-existing condition, or a procedure required by the Clinical Protocol, without a serious deterioration in health, is not considered to be a serious adverse event.

### 6.1.3 Device Malfunction

A device malfunction (DM) is the failure of a device to meet its performance specifications or otherwise perform as intended, when used in accordance with the IFU or protocol.

## **6.2 Device, Process or Procedure Relationship**

Determination of whether there is a reasonable possibility that a product, process or procedure caused or contributed to an AE is to be determined by Study Staff and recorded on the appropriate CRF. Determination should be based on assessment of temporal relationships, evidence of alternative etiology, medical/biologic plausibility, and patient condition (pre-existing condition).

### **6.2.1 Unanticipated (Serious Adverse) Device Effect [U(S)ADE]**

Unanticipated serious adverse device effect (USADE) refers to any serious adverse effect on health or safety or any life-threatening problem or death caused by, or associated with, a device, if that effect, problem, or death was not previously identified in nature, severity, or degree of incidence in the protocol or application (including a supplementary plan or application), or any other unanticipated serious problem associated with a device that relates to the rights, safety, or welfare of participants. See Anticipated Device Effects ([Section 12.2](#)).

## **6.3 Adverse Event/Device Deficiency/Product Experience Reporting**

### **6.3.1 Adverse Event Reporting**

Occurrences of adverse events will be monitored for each participant during the course of the study as required by this protocol, per AE and SAE definitions as noted in the sections above.

All information must be entered in the Electronic Data Capture (EDC) system as soon as feasible. AEs need to be collected for consented participants on the appropriate AE CRF. Additional information with regards to an adverse event, including whether or not the event was anticipated, should be updated within the appropriate CRF and source records.

Serious adverse events (SAEs) that occurred in the user or persons other than the study participant should not be entered in the CRF; they should be reported to [[contact]](mailto:[contact]). Study staff will regularly monitor this email address and will investigate all events reported. These will be reported as soon as possible but no later than 3 calendar days from the day the study personnel became aware of the event. The SAE will be reported to the local IRB according to reporting requirements.

### **6.3.2 Unanticipated Serious Adverse Device Effect Reporting**

iRhythm (the Sponsor) is required to report and document any USADE as soon as possible, but at least within 24 hours of the Investigator's knowledge of the event.

### **6.3.3 Device Deficiency/Device Malfunction Reporting**

All device deficiencies/malfunctions should be reported on the appropriate CRF no later than 3 calendar days from the day the study personnel became aware of the event or as per the investigative location's local requirements, if the requirement is more stringent than those outlined.

An email address ([[contact]](mailto:[contact])) will be made available to allow the Investigator to report device deficiencies/malfunctions. This does not replace the CRF. All information must still be entered in the CRF as soon as feasible. Study staff will regularly monitor this email address and will investigate all events reported.

In case a device deficiency/malfunction occurred before the patient ID has been assigned, the device deficiency should also be reported to iRhythm via [[contact]](mailto:[contact]).

The device, if not applied or not remaining on the participant, should be returned to iRhythm Technologies, Inc.

Device deficiencies/malfunctions should be reported to the IRB per the investigative location's local requirements and IRB requirements.

#### **6.3.4 Adverse Event Reporting to Country Regulatory Authorities by the Sponsor**

Where required by local or regional requirements, the Sponsor will report the SAEs and DDs to the appropriate regulatory authority.

### **7.0 STATISTICAL ANALYSIS**

#### **7.1 Analysis Population**

Following the Phase I completion of all participant activities an analysis will be conducted. Separately, following the Phase II completion of all participant activities an analysis will be conducted. All analyses will be performed on the population of enrolled participants in whom patch application was attempted in that Phase. Phase 1 analysis is considered separate from Phase 2 and will be conducted and reported accordingly. Sections 7.2 and beyond (detailed below) will adhere to this plan.

#### **7.2 Sample Size Calculations and Assumptions**

A prior study of 30 subjects instructed to wear the Zio monitor device up to 30 days resulted in a mean wear time of  $>24$  days ( $24.9 \pm 9.3$  days).

Therefore, a power analysis was performed using the following assumptions:

- Performance goal:  $> 21$  days
- Estimated wear duration with the Zio monitor patch: 24.0 days
- Estimated standard deviation of wear duration with the Zio monitor patch: 9.3 days
- Statistical test: One sample t-test
- Statistical Power: 80%
- Significance level: One-sided alpha = 0.05

Given these assumptions, enrollment of 61 participants is required to assess performance of wear duration performance.

SAS Enterprise Guide 8.3 was used for all calculations.

In order to assess the frequency of adverse events with reasonable precision, and to account for the possibility that up to 25% of enrolled participants may not provide ECG data at the 30-day visit due to device removal or loss to follow-up, enrollment of up to 75 participants is planned for each of the two (2) phases. Seventy-five participants have already been enrolled in the first phase of this study which utilized the iRhythm legacy skin preparation process. An additional 75 participants will be enrolled utilizing an updated skin prep process. A total of 150 participants will be enrolled under this protocol

#### **7.3 Planned Interim Analyses**

There is no planned interim analysis for this study. Each analysis will be considered the final analysis for that Phase of the study.

#### **7.4 Statistical Analyses**

For wear duration performance, mean wear duration, standard deviation and 95% confidence interval will be reported. For analyzable time performance, the mean percent analyzable time, standard deviation, 95% confidence interval, and percentage of patients with analyzable time  $>80\%$  will be reported. Performance objectives will be met if the mean wear duration is greater than 21 days, and percent analyzable time is greater than 80% in 90% of subjects.

For other analyses, mean and standard deviation or median, interquartile range, minimum and maximum will be reported for continuous variables; counts and percentages will be reported for categorical variables.

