## PROTOCOL SUMMARY

Protocol Number	IRT-003-2024
Title	Validation Study: Extended Wear Performance of the Zio monitor  – SHASTA II
Objective	
To evaluate the wear performance of the Zio monitor device in a representative population over an extended wear period (of up to 30 continuous days) to demonstrate that the device can be worn with adequate patch adherence and signal quality through 21 days.
 
Assessment of wear performance will include evaluation of the wear duration of the patch and percentage of analyzable electrocardiographic time.
 
Product safety will be assessed by collection of all adverse events.

Study Device	Zio monitor
Targeted Number of Participants	A total of up to 150 participants will be enrolled at US iRhythm locations. The study may enroll participants from the community surrounding San Francisco, CA and Deerfield, IL as referred by FieldWork® (or another recruitment vendor) at the iRhythm clinic in those locations.
Study Design	A prospective, multi-center, single-arm study to validate the design of the Zio monitor/Zio MCT device form factor in extended (21-day) wear when utilizing an updated skin prep process.
Performance Objectives and Measures	
Performance Objectives
 
Mean wear duration and percent analyzable time of the Zio monitor will be assessed. Performance goals include mean wear duration of 21 days and percent analyzable time of 80%.
 
Performance objectives will be met if the mean wear duration is greater than 21 days, and percent analyzable time is greater than 80% in 90% of subjects.
 
Safety Measures
 
The proportion of participants that experience clinically significant skin irritation through 30 days of wear will be assessed through capture and reporting of all adverse events.

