The study device includes the wearable ECG adhesive assembly and symptom button common to both the Zio monitor and next generation Zio AT (Zio MCT) ambulatory cardiac monitoring devices. The gateway associated with Zio MCT necessary for transmission of ECG data during device wear will not be included as part of this study. For simplicity, the study device will be referred to Zio monitor within this protocol. Additional information regarding the study device is included in Section 2.3.

The Zio monitor device should not be submerged in water. During a bath, keep the device above water. Please refer to the Zio monitor application instructions for the full set of details.

Additionally, the percentage of analyzable ECG signal (i.e., percent analyzable time) will be assessed against a performance benchmark of 80%. The device tested in this extended wear study will be the design cleared in K202359, with minor improvements for manufacturability and with the programming configurations updated to allow for continuous ECG data recording for up to 30 days. Performance objectives include a mean wear time of at least 21 days, and percent analyzable time (i.e., artifact-free ECG signal) greater than 80% for at least 90% of study participants.

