## **3.0 STUDY PERFORMANCE OBJECTIVES AND ADDITIONAL MEASURES**

### **3.1 Wear Time Performance Objective**

Wear duration is defined as the number of days the patch is attached to the participant. Wear duration measurement will start at the time of device application and will end at any of the following events:

- the device is removed at the 30-day follow-up visit, or
- the device fails to adequately adhere to the skin.

All enrolled participants on whom patch application was attempted will be included as part of the mean wear duration analysis. However, participants who discontinue wear of the device for reasons outside of the study protocol, or occurrence of an adverse event not related to the study, will not be counted in the analysis. Full disclosure for reasons of discontinuation will be provided in the study report.

Mean wear duration will be compared to a performance goal of 21 days. The performance objectives will be met if the mean wear duration is greater than 21 days.

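### The wear success rule compares the observed mean with 21 days and does not use the one-sided 5% t-test on which each phase was sized

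*Protocol*

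**What the plan says.** All references are to protocol version 02.

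- **Sizing.** Section 7.2 lists "Statistical test: One sample t-test" and "Significance level: One-sided alpha = 0.05", with 80% power, a goal of 21 days, an expected mean of 24.0 days and an SD of 9.3 days. It arrives at 61 participants and plans up to 75 per phase.
- **Decision rule.** Section 7.4: "Performance objectives will be met if the mean wear duration is greater than 21 days, and percent analyzable time is greater than 80" (per cent, for nine-tenths of subjects). Section 3.1: "The performance objectives will be met if the mean wear duration is greater than 21 days". The Protocol Summary: "Performance objectives will be met if the mean wear duration is greater than 21 days". None of the three names a test, a p-value or a confidence limit.
- **Interval.** Section 7.4 says that "mean wear duration, standard deviation and 95% confidence interval will be reported". The interval has no part in the decision.
- **A further wording.** Section 2.0: "Performance objectives include a mean wear time of at least 21 days".
- **Two phases.** Section 7.1: "Phase 1 analysis is considered separate from Phase 2 and will be conducted and reported accordingly". Section 7.3 treats each as the final analysis of its phase.

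**The concern.** A test at one-sided 5% and a check that the observed mean exceeds 21 are different criteria. The test asks the mean to clear the goal by a margin that covers sampling error. The check asks for no margin, so a device performing exactly at the goal passes about as often as it fails. The protocol states alpha and power for the first criterion and writes its success rule as the second.

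At stake is the verdict on one of the two objectives that support the 21-day wear claim. With two readings available, a mean of 22 days could be reported as success under section 7.4 and as non-significant under section 7.2. Because each phase has its own final analysis, the question arises twice. The point concerns wear only, since section 7.2 gives no alpha or power for analyzable time.

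**Working it through.** **Inputs, all from section 7.2:** goal 21 days; expected mean 24.0 days, so the difference is 3.0; SD 9.3; one-sided alpha 0.05; n = 61 required, up to 75 planned per phase.

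**1. The plan's own figure.** Power of the one-sample t-test is P(T > t(0.95, n−1)), where T is noncentral t with n−1 degrees of freedom and noncentrality 3 × √n / 9.3.

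- n = 60: 79.5%
- n = 61: noncentrality 2.519, power 80.1%
- n = 75: noncentrality 2.794, power 86.9%

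So 61 is the correct number for the test named in section 7.2.

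**2. Standard errors.** 9.3/√61 = 1.191 days; 9.3/√75 = 1.074 days.

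**3. Observed mean that the t-test needs** (observed SD equal to 9.3): 21 + t(0.95, n−1) × SE.

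- n = 61: 21 + 1.671 × 1.191 = 22.99 days
- n = 75: 21 + 1.666 × 1.074 = 22.79 days

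Means from 21.0 up to these values get opposite verdicts. For example, an observed mean of 22 gives t = 1/1.191 = 0.84 and one-sided p = 0.20 (n = 61), or t = 1/1.074 = 0.93 and p = 0.18 (n = 75).

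**4. Chance of meeting the wear objective.** Literal rule: Φ((true mean − 21)/SE), by normal approximation. Test: noncentral t as in step 1.

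| True mean (days) | Literal, n=61 | t-test, n=61 | Literal, n=75 | t-test, n=75 |
|---|---|---|---|---|
| 20 | 20.1% | 0.7% | 17.6% | 0.5% |
| 21 | 50% | 5% | 50% | 5% |
| 22 | 79.9% | 20.8% | 82.4% | 23.5% |
| 24 | 99.4% | 80.1% | 99.7% | 86.9% |

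**5. Does the 50% depend on normality?** Wear is capped at about 30 days, so this was simulated with a true mean of 21.

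- Scaled beta on 0 to 30 days, SD 9.3: the observed mean exceeds 21 in 50.7% of trials (n = 61) and 50.5% (n = 75).
- 40% of participants at 30 days and the rest uniform on 0 to 30 (SD about 9.9): 50.6% and 50.8%. In this second model the nominal 5% t-test rejects in about 6% of trials.

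**6. Could the reported 95% interval be the deciding one?** A two-sided 95% interval with its lower end above 21 is a one-sided 2.5% test. Its power at a true mean of 24 is 69.8% (n = 61) or 78.7% (n = 75), so it does not match the sizing either.

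**7. Does requiring both objectives repair it?** Assume a true mean wear of 21 and independent objectives, and take at least 90% of subjects as at least 68 of 75 or 55 of 61. The joint pass rate is 0.5 × P(X ≥ 68), with X binomial(75, p). The protocol gives no value for p, so a range is shown:

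- p = 0.90: 0.5 × 0.521 = 26%
- p = 0.95: 0.5 × 0.966 = 48%
- p = 0.98: 0.5 × 0.9999 = 50%

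At n = 61 and p = 0.90 it is 0.5 × 0.590 = 29%. The second objective does not bring the rate near 5%.

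**The case against.** The strongest reply is that sections 7.2 and 7.4 are one plan. Section 7.2 names the goal, the test, the side and the alpha; section 3.1 says the mean is compared with that same goal; section 7.4 then states the goal briefly. On that reading the rule is shorthand, alpha is 5% and power is 80.1%. A statistical analysis plan, not seen here, may say so. This reading is possible and cannot be excluded. But the protocol does not defer the rule: it states it in three places, each time as a bare comparison of the mean with 21. A later document that applies the t-test would still have to be reconciled with that wording.

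Three smaller points stand:

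- Under the literal rule power is exceeded, not lost. The harm is false passes.
- The difference between at least 21 and greater than 21 is immaterial for a continuous mean. The wording in section 2.0 adds little evidence of intent.
- Phase I data collection was over before version 02. Enrolment was complete by 28 February 2025 (section 5.1), the 33-day limit runs to about 2 April, and version 02 is dated 23 April 2025. For Phase I the rule can no longer be clarified prospectively.

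**Conclusion.** The concern holds: the rule is wrong as written. The sample size of 61 is right for the test in section 7.2, but the stated success rule does not use that test and does not have its error rates. Read literally, the false-pass rate at a true mean of 21 days is about 50% against the stated 5%, and the pass rate at 24 days is 99.4% against 80.1% (n=61). The two readings disagree over a band of about 2 days of observed mean, against an assumed margin of 3 days. The 50% hardly depends on the SD or on normality. The other figures assume SD 9.3 and an approximately normal mean. If the shorthand reading is intended, the error rates are as stated and only the wording is at fault. Because pass or fail turns on which reading is used, the text must settle it.

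**What to change.** In the Protocol Summary and sections 3.1 and 7.4, write:

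> *The wear objective is met if the one-sample t-test of mean wear duration against 21 days is significant at one-sided alpha 0.05, that is, if the lower one-sided 95% confidence limit (the lower end of the two-sided 90% interval) exceeds 21 days.*

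Align section 2.0 with it. In section 7.4, say that the two-sided 95% interval is descriptive, so that it is not taken for the deciding limit. N = 61 and 80.1% power then stand, provided 61 participants contribute wear data. If the 25% loss that section 7.2 allows for ECG data also applied to wear, 75 × 0.75 leaves about 56 and power is 77.0%.

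If an observed-mean benchmark is really intended, say so and withdraw the alpha and power statement in section 7.2.

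As a clarification only, state that the 80% power covers wear alone. If the 90%-of-subjects criterion is meant as an observed rate, say that too; an exact interval would show its precision (68 of 75 gives 81.7% to 96.2%).

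**Cost.** Wording only, with no added participants or data. The pass mark rises: at SD 9.3, observed means between 21.0 and about 23.0 days (n = 61) or 22.8 days (n = 75) would no longer count as success. Any change to the Phase I rule must be disclosed as made after data collection. For Phase II the change should be made before its data are seen.
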